The research coordinator will then complete page one of the Ketamine Data Form. This includes the participant's medical history, including a history of drug abuse, or prior narcotic use, a description of the injury, prior medications given to the subject for this injury either by EMS or in the emergency department, baseline vital signs (prior to study drug administration) and the time of study drug administration. Page 2 includes the baseline (pre study drug administration) visual analog pain scale that the participant will complete.

MEDICATION ADMINISTRATION

If the participant has not yet had an IV placed, one will be placed by the nurse caring for the participant at this time. Study drug will then be administered.

VITAL SIGN COLLECTION

The participant's heart rate, blood pressure, respiratory rate and oxygenation saturation (by pulse oximetry) will be collected every 5 minutes for the first 30 minutes, and every 10 minutes

for the next 30 minutes. The study will terminate at the end of 60 minutes and a final set of vital signs will be recorded at that point on Page 3 of the Ketamine Data Form.

REEVALUATION & EXIT SURVEY

The participant will be asked to complete repeat visual analog pain scales at 15, 30, and 60 minutes following study drug administration. The VAS will be administered by a second study coordinator, who has been blinded to the vital sign information, since blood pressure response may allow unblinding to occur. The participant will not have access to their original score for comparison. The study coordinator will then complete the post treatment survey on Page 5. The participant will continue to receive standard care by the emergency department physicians and nurses to ensure adequate relief of pain, appropriate treatment of the underlying pathology, hemodynamic and neuropsychiatric stability, and appropriate diagnostic evaluation, disposition, and follow-up. Any adverse events that occur during the continued treatment of the participant until either admission or discharge will be recorded.

RESCUE MEDICATION

Subjects that do not obtain adequate pain relief within 15 minutes of study drug administration will be offered rescue medication with intravenous morphine sulphate at the same weight-based dose (0.01mg/kg; maximum 10 mg)

TREATMENT OF ADVERSE EVENTS AND SERIOUS ADVERSE EVENTS

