Patients who are identified as potential study participants will be approached by the research coordinators regarding informed consent. The purpose of the study, study procedures, and associated risks and benefits will be explained to the potential subject. Following this, subjects will have 10 minutes to review the consent form on their own and if they agree to participate in the study, the consent form will be completed.

2.f Randomization Method and Blinding

Randomization will occur in the research pharmacy using opaque, sealed envelopes. Twenty participants will be randomized into each arm. Participants in the LDK arm will receive 0.4 mg/kg IV of ketamine (40 mg maximum). Participants in the opioid arm will receive 0.1 mg/kg of morphine up to 10 mg. Medications will be prepared by the pharmacy and delivered to the treating nurse in identical syringes. Study drug will be blinded to the research team and the study participant.

2.g Risks and Benefits

Patient will be exposed to medical risks in both conditions. Patients exposed to morphine will be at risk for hypotension, respiratory depression, altered mental status and possible allergic reaction. Patients exposed to ketamine will be at risk for hypertension, dysphoria and in rare cases laryngospasm and emergence reaction. These side effects are well known by practitioners since both of these drugs are regularly given in the Emergency Department. Patients may also be at risk for inadequate pain control in either condition.

2.h Early Withdrawal of Subjects

Participants will be told they have the right to withdraw from the study at anytime for any reason. Participants will also be taken out of the study early if the physician, nurse or research coordinator decides that the participant is at risk for a life-threatening event. Since this study does not include any outpatient follow-up, we do not anticipate early withdrawal to be a problem.

2.i When and How to Withdraw Subjects

The research coordinator will continually monitor the participant, and the nurses and physicians will be able to remotely monitor the participant's vital signs at the telemetry station. If a life-threatening event is identified, the participant will be resuscitated as deemed appropriate by the physician caring for the participant.

2.j Data Collection and Follow-up for Withdrawn Subjects

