Participants will be identified in the Emergency Department waiting room as a potential candidate for the study by nurses, physicians and the research coordinator on duty. If a long bone fracture is deemed highly likely or if a long bone fracture has been identified by X-ray, the injury occurred within 24 hours, and the patient is conscious and alert and hemodynamically stable they will be approached for consent.

F2 Schedule of Measurements

Participants will have vital signs collected immediately prior to administration of the medication to which they are assigned. Vital signs (heart rate, respiratory rate, blood pressure, and pulse oximetry) will be recorded every 5 minutes for the first 30 minutes following the administration of study drug, and then every 10 minutes until study

completion (60 minutes post medication administration). Pain severity will be assessed immediately prior to administration of medication via the VAS and at 15, 30 and 60 minutes following medication administration..

F3 Visit 1

The participant will only be treated on the first encounter in the Emergency Department.

F4 Visit 2 etc.

N/A

F5 Safety and Adverse Events

We will monitor and record for changes in vital signs including hypotension, hypertension, tachycardia, bradycardia, respiratory depression. We will also monitor for nausea and vomiting, laryngospasm, and emotional and psychological effects (emergence reactions).

5.a Safety and Compliance Monitoring

Participants will receive only one dose of study drug, thus compliance will not be an issue. Participants will be monitored continuously for alterations in vital signs, or any other adverse events during the entirety of the study.

5.b Medical Monitoring

Both of these medications are commonly used in the emergency department setting, and have a good safety record. Nonetheless, AEs, and SAEs may occur. Any adverse event directly linked to administration of either ketamine or morphine that results in permanent disability or death will result in the cessation of the entire study.

Further, after every 10 patients are enrolled, all AE's will be reviewed by an independent expert. If there is a high frequency of adverse events that cause great distress to participants or that results in many participants ending their participation, the study will be terminated.

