Based on past research, we believe adverse events will be rare and severe events are unlikely to occur.

5.e Data Collection Procedures for Adverse Events

The research coordinator will write down all adverse events on the data form in the designated spot. They will also report the events to the treating team.

5.f Reporting Procedures

The research coordinator will report all adverse events to the principal investigator (PI) investigator during the study. The PI will determine severity and causality. The PI will keep track of adverse events to determine if the study needs to be stopped.

5.g Adverse Event Reporting Period

This is an acute treatment trial, with a duration of one hour following study drug administration. However, any AEs that occur at any time during the entire ED stay of the study participant will be reported.

Post-study Adverse Event

The duration of the drugs used in this study will not exceed the time the participant is monitored.

F6 Study Outcome Measurements and Ascertainment

Study outcomes involve change in participants' pain as measured by the VAS, significant changes in any vital signs collected, a list of adverse events that the participant experienced, as well as questions included in the data form assessing whether the participant would consider using the drug given to them for pain relief in the future.

G Statistical Plan

G1 Sample Size Determination and Power

Sample size for this study is based on limited funding and will serve as a pilot study looking for trends in the efficacy of morphine and ketamine to treat pain as well physiologic effects and adverse events. If the results appear promising, further funding will be requested and a full power analysis will be performed.

G2 Interim Monitoring and Early Stopping

All adverse events will be promptly reviewed by the primary research team following the participant's completion of the study. Any adverse event directly linked to administration of either ketamine or morphine that results in permanent disability or death will result in the cessation of the entire study. After every 10 patients are enrolled, adverse event information will be reviewed by an independent expert. If there is a high frequency of

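### F6 names change in VAS as the efficacy outcome, but the visible text states no baseline adjustment, although a pre-dose VAS is scheduled for every participant

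*SAP*

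**What the plan says.** SAP section F6 opens its list of outcomes with "Study outcomes involve change in participants' pain as measured by the VAS". It then lists vital-sign changes, adverse events and a question on future use of the drug. It names no time point, test, model or covariate for comparing "pain as measured by the VAS" between the arms.

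The baseline score is planned twice over. In E1 the data form is described thus: "Page 2 includes the baseline (pre study drug administration) visual analog pain scale that the participant will complete". F2 agrees: "Pain severity will be assessed immediately prior to administration of medication via the VAS". Participants then "complete repeat visual analog pain scales at 15, 30, and 60 minutes following study drug administration" (E1, reevaluation and exit survey).

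Section 2.f gives the size: "Twenty participants will be randomized into each arm". G1 explains it: "Sample size for this study is based on limited funding and will serve as a pilot study". No alpha, power, effect size or VAS SD is given. If results look promising, "further funding will be requested and a full power analysis will be performed".

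The text at hand breaks off in mid-sentence within G2, so any later analysis section in G cannot be seen.

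**The concern.** If change in VAS is compared between arms with no covariate, the analysis subtracts the whole baseline score, which fixes the slope of follow-up on baseline at 1. The true slope is usually below 1. The excess subtraction then adds noise, and a chance difference in baseline pain feeds into the arm contrast.

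This matters more than usual here. The sample is set by funding and cannot easily grow, and the pilot's purpose is to look for trends that would justify a larger study. The width of the interval around the arm difference is therefore its main statistical product. The covariate that could narrow that interval is already scheduled for every patient. If the choice between adjusted and unadjusted results is left open until the data are unblinded, it can also be made with the results in view.

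**Working it through.** **No figure of the plan to reproduce.** The size of 20 per arm (2 × 20 = 40) rests on funding, with no inputs behind it. The check compares two analyses of the same 40 patients.

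**Inputs.** From the SAP: n = 20 per arm and one pre-dose VAS each. Assumed, because the SAP does not give them: correlation r between baseline and follow-up VAS, and ratio k of follow-up SD to baseline SD (s). A linear, roughly normal model and complete data are also assumed.

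**Per-patient variances.**
- Unadjusted change: s²(1 + k² − 2rk).
- Follow-up VAS adjusted for baseline: s²k²(1 − r²).
- First minus second: s²(1 − rk)², which is never negative.

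Before the cost of estimating the slope, adjustment therefore cannot be less precise. With one covariate and N = 40, that cost multiplies the variance by about 1 + 1/(N − 4) = 1 + 1/36 = 1.028. The expected loss is thus at most 2.8% of variance, or about 1.4% of the standard error (√1.028 = 1.014).

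**Equal SDs (k = 1).** The ratio of variances is (1 − r²)/[2(1 − r)] = (1 + r)/2. The penalised ratio is (1 + r)/2 × 1.028. The last column is 40 divided by the penalised ratio.

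| r (assumed) | (1 + r)/2 | Penalised ratio | Simulated ratio | 95% CI width ratio | Patients an unadjusted change score would need |
|---|---|---|---|---|---|
| 0.3 | 0.65 | 0.67 | 0.665 | 0.82 | about 60 |
| 0.5 | 0.75 | 0.77 | 0.771 | 0.88 | about 52 |
| 0.7 | 0.85 | 0.87 | 0.871 | 0.94 | about 46 |
| 0.9 | 0.95 | 0.98 | 0.981 | 0.99 | about 41 |
| 0.95 | 0.975 | 1.00 | 1.000 | 1.00 | about 40 |

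The simulation used 20,000 trials of 20 per arm at each r. Break-even solves (1 + r)/2 × 37/36 = 1, so r = 72/37 − 1 = 0.946.

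**Half-width at r = 0.5, k = 1.** With t on 38 df, the change score gives 2.02 × √(1 × 2/20) = 0.64 SD. With t on 37 df, the adjusted analysis gives 2.03 × √(0.771 × 2/20) = 0.56 SD.

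**Unequal SDs, penalty included.**

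| k | r = 0.3 | r = 0.5 | r = 0.7 |
|---|---|---|---|
| 0.7 | 0.43 | 0.48 | 0.50 |
| 1.5 | 0.90 | 0.99 | 1.03 |

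**Chance imbalance.** The standard error of the baseline mean difference is √(2/20) = 0.32 SD, and about one trial in three exceeds it in absolute size. At r = 0.5 and k = 1, an imbalance of 0.32 SD moves the change-score contrast by (1 − 0.5) × 0.32 = 0.16 SD in favour of the arm that started with more pain. The standard error of that contrast is √(2 × 0.5 × 2/20) = 0.32 SD, so the shift is half a standard error.

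**The case against.** The strongest objection is that F6 defines an outcome and not an analysis. A reader might infer that the plan commits to a raw, unadjusted change score. The text does not support that. It uses neither word, and naming change as the outcome leaves room for a baseline covariate: with pre-dose VAS in the model, follow-up VAS and change in VAS give the same treatment estimate. F6 could stand as it is. The place where a model would normally appear comes after the text stops, so adjustment elsewhere cannot be excluded. All of this stands, and it makes the point conditional on what the unseen text says.

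A reader might also infer that adjustment is sure to tighten the comparison. The documents do not give r or k, so they cannot show that. At k = 1.5 there is almost no gain at r = 0.5 and a slight loss at r = 0.7. This stands too, but the expected loss is bounded at about 3% of variance whatever r and k are.

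Two further inferences fail. A change score does not throw the baseline away; it uses it with a weight that is generally not optimal. And nothing shown suggests that optional fentanyl before dosing would unbalance the arms systematically. The pre-dose VAS is taken after it, and under randomization an unadjusted change score is unbiased on average. What adjustment addresses is precision, and chance imbalance in a trial that is run once.

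Finally, some 30- and 60-minute scores may follow rescue morphine, which is offered when relief at 15 minutes is inadequate (E1), and some follow-up scores may be missing (2.j). The objection that baseline adjustment solves neither is correct.

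**Conclusion.** The point holds as a near-costless improvement. It is not an error in any stated figure. In the visible text, change in VAS has no baseline adjustment and no named time point, while the covariate is scheduled for everyone.

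Against an unadjusted change-score comparison with 20 per arm, equal SDs and an assumed correlation of 0.3 to 0.7, adjustment removes about 33% to 13% of the variance of the arm difference, so the confidence interval is about 18% to 6% narrower. The gain is larger if the follow-up SD is smaller than the baseline SD. It disappears near a correlation of 0.95 with equal SDs, or sooner if the follow-up SD is larger. If a section after G2 already specifies baseline adjustment, that part of the point falls away.

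**What to change.** Unless a later section already does so, add to F6 or G that the arms are compared with a linear model for VAS (or change in VAS) at a named time point, with treatment and pre-dose VAS as terms. State that the adjusted mean difference is reported with its 95% CI and that unadjusted change by arm is shown as a descriptive summary. Settle the model and time point before unblinding.

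The cost is a sentence or two and one degree of freedom, with no new data or procedures. How missing scores and scores taken after rescue medication enter the analysis needs its own statement, because this change does not cover it.

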Due to the short duration of the study (60 minutes), we do not anticipate early withdrawal to be a problem. Participants who have inadequate pain relief and require rescue medication, or who have adverse events that require other treatment will have their data included, even if study personnel are unable to complete the follow-up VAS scores at 15, 30, or 60 minutes.

Study Drug

2.k Description

Ketamine is a dissociative agent that is thought to modulate pain by binding to NMDA receptors. Participants assigned to the ketamine arm will be given 0.4 mg/kg IV of ketamine (40 mg maximum).

Morphine is an opioid that acts on opioidergic receptors to modulate pain. Participants in the opioid arm will receive 0.1 mg/kg IV of morphine (10 mg maximum).

2.l Treatment Regimen

The study is designed to compare a one-time dose only. Therefore study medication administration will occur once following the baseline pain and vital sign assessment.

Assignment of Subjects to Treatment Groups

Participants will be assigned to either the ketamine arm or the morphine arm in the pharmacy by random number generator. Participants and all study personnel will be blinded to the assignment.

2.m Preparation and Administration of Study Drug

Once participants are in the process of being consented, the pharmacy will be notified to prepare the drug. The drug will then be sent to the Emergency Department for administration.

2.n Subject Compliance Monitoring

Participants will be given the drug intravenously by the emergency department staff nurse assigned to their care. The research coordinator will monitor the participant's vital signs, pain relief, and any side effects during the duration of the study. Since medication is only given one time, non-compliance will not be an issue.

Prior and Concomitant Therapy

Participants will be excluded from the study if they are found to be chronic users of either prescribed or illicit opioids or opiates.

2.o Packaging

Study drug will be packaged by the pharmacy in identical looking syringes so as to maintain blinding. This is a question for the pharmacy. I will email [name] about this.

2.p Blinding of Study Drug

As above

2.q Receiving, Storage, Dispensing and Return

The pharmacy will transport the study medication to the emergency department. If the patient withdraws from the study, the medication can be returned to the pharmacy.

F Study Procedures

F1 Screening for Eligibility

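### In rescued participants, the future-use answer (F6) is collected after rescue morphine as well as study drug, so it may not reflect the study drug alone

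*SAP*

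**What the plan says.** **Outcome.** SAP F6 lists pain change on the VAS, vital-sign changes, adverse events, and data-form questions "assessing whether the participant would consider using the drug given to them for pain relief in the future".

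**Timing.** SAP E1 (Reevaluation & Exit Survey) has the participant complete "repeat visual analog pain scales at 15, 30, and 60 minutes following study drug administration". It continues: "The study coordinator will then complete the post treatment survey on Page 5".

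**Rescue.** SAP E1 (Rescue Medication): "Subjects that do not obtain adequate pain relief within 15 minutes of study drug administration will be offered rescue medication". The rescue agent is "intravenous morphine sulphate at the same weight-based dose (0.01mg/kg; maximum 10 mg"). It is the same agent in both arms.

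**Blinding.** SAP 2.f: "Study drug will be blinded to the research team and the study participant".

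**Handling of rescued participants.** SAP 2.j: "Participants who have inadequate pain relief and require rescue medication, or who have adverse events that require other treatment will have their data included". The text available has no separate rule for their survey answers.

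**Aim.** SAP 2.l says that the comparison is of a single dose of study medication.

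**The concern.** F6 speaks of one drug, and 2.l describes a comparison of single doses. By the time of the survey, a rescued participant has had two injections for pain. In the ketamine arm these are a blinded syringe of ketamine and then morphine, which is the comparator. In the morphine arm they are morphine and then more morphine. An opinion given at the end can carry over from the second injection to the first, and what carries over differs by arm.

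The VAS has a 15-minute reading at about the time rescue is first offered. For the future-use questions the plan describes only the end-of-study survey, so no pre-rescue answer is planned. At stake is the meaning of one listed outcome in those participants for whom the study drug did not give adequate relief.

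**Working it through.** The plan states no figure for this outcome, no rescue rate and no power calculation (G1 bases the sample size on funding). There is nothing to reproduce, so the check is a timeline followed by an illustration on assumed values.

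**Timeline, minutes after study drug (E1)**

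- 0: blinded study drug.
- 15: first repeat VAS; rescue is offered if relief is inadequate by then.
- 30 and 60: further VAS.
- After 60: post-treatment survey.

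The longest gap from rescue to survey is about 60 − 15 = 45 minutes.

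**How many answers could be affected.** With 20 per arm (2.f) and assumed rescue rates of 10%, 25%, 50% and 75%, the answers given after both injections number 2, 5, 10 and 15 of 20. One participant is 1/20 = 5 percentage points.

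**Effect on the comparison.** Let b be the yes-rate for the study drug alone, r the rescue rate and q the yes-rate actually given by rescued participants. Then

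observed yes-rate = b(1 − r) + q·r.

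*Case A: no true difference, b = 50% in both arms, and the same q in both arms.*

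| Rescue, ketamine / morphine | q | Ketamine | Morphine | Difference |
|---|---|---|---|---|
| 50% / 25% | 80% | 0.250 + 0.400 = 65.0% | 0.375 + 0.200 = 57.5% | +7.5 |
| 50% / 25% | 20% | 0.250 + 0.100 = 35.0% | 0.375 + 0.050 = 42.5% | −7.5 |
| 75% / 25% | 80% | 0.125 + 0.600 = 72.5% | 57.5% | +15 |
| 75% / 25% | 20% | 0.125 + 0.150 = 27.5% | 42.5% | −15 |
| 25% / 25% | 80% | 57.5% | 57.5% | 0 |

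With 20 per arm, 7.5 points is 1.5 participants and 15 points is 3.

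*Case B: equal rescue of 25%, b = 50%, but rescue shifts answers only in the ketamine arm, where it is a different drug.* With q = 80% for ketamine and 50% for morphine, the result is 57.5% against 0.375 + 0.125 = 50.0%, a difference of +7.5. With q = 20% for ketamine it is 42.5% against 50.0%, or −7.5. Equal rescue rates do not by themselves protect the comparison.

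*Case C: a true difference exists.* Assume 80% yes without rescue. Among rescued participants, assume 30% would say yes about the study drug alone but 70% say yes after morphine. Rescue is 60% in one arm and 20% in the other.

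- Study drug alone: 0.4 × 0.8 + 0.6 × 0.3 = 50%, against 0.8 × 0.8 + 0.2 × 0.3 = 70%. The difference is 20 points.
- Observed: 0.4 × 0.8 + 0.6 × 0.7 = 74%, against 0.8 × 0.8 + 0.2 × 0.7 = 78%. The difference is 4 points.

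The sign and size follow from q and r, and the document fixes neither.

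**Rescue dose.** E1 calls the rescue the same weight-based dose but writes 0.01 mg/kg, while E1, 2.f and 2.k give morphine as 0.1 mg/kg. These differ by 0.1 / 0.01 = 10 times. The amount of rescue morphine behind these answers is therefore undefined until the passages are reconciled.

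**The case against.** **The form is not visible.** F6 paraphrases the questions, and no passage says that they are on Page 5. The item may already name the study medication. This stands as a limit. The end-of-study survey is, however, the only survey the plan describes, and the plan's own text leaves the reference open.

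**Participants can tell two injections apart.** The plan calls one the study drug and the other rescue medication, so F6 most naturally means the former. This also stands. A reader might infer that rescued participants cannot know which drug is meant, but the document does not show that, nor does it say that they are told the rescue is morphine. What remains is carry-over of opinion, which does not require confusion.

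**The direction is assumed.** A reader might infer that rescue flatters whichever arm needs more of it. That holds only if relief after morphine raises approval. If a failed first injection sours the answer, the sign reverses, as Case A shows.

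**The answer may be meant to cover the whole experience, rescue included.** The inclusion rule in 2.j is compatible with that, but the single-dose aim in 2.l and the singular drug in F6 point the other way. The available text ends within G2, so a later analysis rule cannot be excluded.

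**Asking before rescue would be worse.** Rescued participants would answer from about 15 minutes, while in pain, and everyone else at 60 minutes. Timing would then depend on outcome and on arm, and later effects of the study drug would be missed. This stands, and a common time is the better choice.

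**The stakes are small.** A reader might infer that this outcome drives the decision to seek further funding. G1 ties that decision to promising results but names efficacy for pain, physiologic effects and adverse events, not preference.

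**Conclusion.** The point holds for rescued participants only. Their planned answer follows both the blinded study drug and, where rescue was given, intravenous morphine, so it may not reflect the study drug alone. Because rescue means a different drug in one arm and more of the same in the other, the between-arm comparison can be distorted. The direction and size are unknown; the 7.5 to 15 points in Case A and the shrinkage from 20 points to 4 in Case C rest entirely on assumed rescue and response rates.

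It would go too far to say that the outcome fails to measure the study drug: answers from participants who are not rescued still refer to it alone. The conclusion rests on the future-use questions being part of the end-of-study survey, and on the form not already limiting them to the study injection. This is a minor matter in a secondary outcome of a pilot, and it does not touch the VAS result.

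**What to change.** 1. In E1 and F6, state that the item refers to the first (study) injection and not to any later rescue medication. Make the data-form item say so if it does not already.
2. Keep the common 60-minute timing for everyone.
3. Report the answer for all randomised participants by arm, with the number rescued beside it. Add a split by rescue status within arm, labelled descriptive: rescue occurs after randomisation, so the split is not a causal comparison.
4. Do not describe rescued participants' answers as a clean preference for the study drug.
5. Separately, reconcile the rescue dose in E1 with the morphine dose given elsewhere in the document.

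For items 1 to 4 the cost is one clarified sentence in two sections, possibly one reworded form item, and one extra table split. Some carry-over of opinion from rescue will remain, which is why item 4 is needed. None of these four items changes treatment, sample size or the VAS schedule.
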